#### 8.1.2. Estimand 1b

#### 8.1.2.1. Main Analysis Approach

A participant receiving any prohibited medication or discontinuing the treatment due to related adverse event or requirement for prohibited medication prior to Week 12 visit will be considered as a non-responder (Composite strategy). If a participant discontinued treatment for reasons other than related adverse event or requirement for prohibited medication, PASI scores after the treatment discontinuation date will be set to missing (Hypothetical strategy). If a participant experienced any treatment interruption, PASI score reported after the treatment interruption will be used as reported (Treatment policy).

Participants without Week 12 PASI score (either due to hypothetical strategy implementation or missed visit) will be considered as non-responder.

The number and proportion of participants with PASI-75 with corresponding 95% CI will be presented by treatment group. The p-value, conditional odds ratio with its corresponding 95% CI, strata-adjusted difference in proportions between treatment groups (DC-608 – Placebo) with its corresponding 95% CI based on the large sample approximation method for binary data using

Mantel-Haenszel strata weights (Mantel, Haenszel 1959) and the Sato variance estimator (Sato 1989) will be presented in the active treatment groups compared to the placebo group.

In addition, a logistic regression model will be performed with PASI-75 at Week 12 as binary response and treatment and baseline PASI score (as a continuous covariate) as covariates on the FAS. The following additional covariates will be tested in the model using backward elimination with a significance level of 0.2 to retain the covariates in the model: age, BMI and weight as continuous covariates, sex, previous biologic therapy (Yes/No) (as per IRT) and geographic region (North America/Western Europe vs. Eastern Europe) (as per IRT) as discrete covariates. At the very least, previous biologic therapy and geographic region will be retained in the model. The conditional odds ratio, with Placebo as reference group, their corresponding 2-sided 95% CI and p-value will be presented.

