# 8.2.3. Proportion of participants achieving ≥50%, ≥75%, ≥90%, and 100% reduction in PASI score (PASI-50, PASI-75, PASI-90, and PASI-100, respectively) at scheduled timepoints (Estimands 5a, 5b, 5c, 5d)

#### 8.2.3.1. Main Analysis Approach

A participant receiving any prohibited medication or discontinuing the treatment due to related adverse event or requirement for prohibited medication will be considered as a non-responder at scheduled timepoints following the event (Composite strategy). If a participant discontinued treatment for reasons other than related adverse event or requirement for prohibited medication, PASI scores reported after the treatment discontinuation date will be treated as missing (Hypothetical strategy). If a participant experienced any treatment interruption, PASI score reported after the treatment interruption will be used as reported (Treatment policy).

Participants without PASI score at each scheduled visit (either due to hypothetical strategy implementation or missed visit) will be considered as non-responder.

The following analyses will be performed using generalized estimating equation (GEE) as an extension of the logistic regression model with treatment, visit and baseline PASI score (as a continuous covariate) as covariates and a treatment by visit interaction. The following additional covariates will be tested in the model using backward elimination with a significance level of 0.2 to retain the covariates in the model: age, BMI and weight as continuous covariates, sex, previous biologic therapy (Yes/No) (as per IRT) and geographic region (North America/Western Europe vs. Eastern Europe) (as per IRT). At the very least, previous biologic therapy and geographic region will be retained in the model. Of note, visits from the earliest timepoint with at least one responder will be included in the model. e.g. if the first responder is on Day 15, all GEE models will include visits from Day 15.

- Participants achieving ≥50% reduction in PASI score (PASI-50) at scheduled timepoints up to Week 12 by treatment group for the FAS. (Estimand 5a)
- Participants achieving ≥75% reduction in PASI score (PASI-75) at scheduled timepoints up to Week 12 by treatment group for the FAS. (Estimand 5b)
- Participants achieving ≥90% reduction in PASI score (PASI-90) at scheduled timepoints up to Week 12 by treatment group for the FAS. (Estimand 5c)

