#### 8.2.5.1.1. Main Analysis Approach

A mixed model repeated measures (MMRM) of percentage change from baseline in PASI score up until Week 12, including terms for treatment, visit, baseline PASI score (as a continuous covariate), a treatment by visit interaction with an unstructured (UN) covariance matrix. The following additional covariates will be tested in the model using backward elimination with a significance level of 0.2 to retain the covariates in the model: age, BMI and weight as continuous covariates, sex, previous biologic therapy (Yes/No) (as per IRT) and geographic region (North America/Western Europe vs. Eastern Europe) (as per IRT) as discrete covariates. At the very least, previous biologic therapy and geographic region will be retained in the model. In case of nonconvergence of the MMRM with UN covariance structure, the first order heterogeneous autoregressive model [ARH(1)] will be fitted instead; if this model still fails to converge then the number of covariance parameters will be reduced further and the first order autoregressive model [AR(1)] will be fitted.

The difference in mean change and mean percentage change between treatments with 95% CI at each scheduled timepoint will be estimated. The data collected after use of a prohibited medication, or discontinuation of treatment for any reason will be set to missing (Hypothetical strategy). The FAS will be used for this analysis. The MMRM analysis will assume a missing-at-random (MAR) mechanism for missing data.

The least-square (LS) mean for change from baseline and percentage change from baseline in PASI score at each time point will be presented for each treatment group until Week 12. Contrasts will be used to compare DC-806 dose regimens versus Placebo at each scheduled visit with the two-sided p-value testing  $H_1$  against  $H_0$ .

For example, at Week 12:

#### Comparison 1

H0:  $\mu$  at Week 12 DC-806 800mg =  $\mu$  at Week 12 Placebo H1:  $\mu$  at Week 12 DC-806 800mg  $\neq \mu$  at Week 12 Placebo

#### Comparison 2

H0:  $\mu$  at Week 12 DC-806 600mg =  $\mu$  at Week 12 Placebo H1:  $\mu$  at Week 12 DC-806 600mg  $\neq \mu$  at Week 12 Placebo

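### Age, BMI, weight and sex enter the adjusted models by backward elimination, so the conditional odds ratio in the logistic and GEE models is not fixed in advance; naming the covariates costs almost no power

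*SAP*

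**What the plan says.** SAP 8.1.2.1 first gives Estimand 1b a conditional odds ratio and a strata-adjusted difference with Mantel-Haenszel weights. It then adds a logistic regression with "treatment and baseline PASI score (as a continuous covariate) as covariates on the FAS". Backward elimination is applied to further covariates, "with a significance level of 0.2 to retain the covariates in the model". The candidates for elimination are "age, BMI and weight as continuous covariates, sex, previous biologic therapy (Yes/No) (as per IRT) and geographic region". Two of them cannot in fact leave: "At the very least, previous biologic therapy and geographic region will be retained in the model". Baseline PASI is in the model statement and is not a candidate. Four covariates are therefore open to selection: age, BMI, weight and sex.

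The same rule appears in two other places:
- **SAP 8.2.3.1**, Estimands 5a-5d: a "generalized estimating equation (GEE) as an extension of the logistic regression model with treatment, visit and baseline PASI score", followed by the same elimination step. SAP 8.2.4.1 applies it to Estimand 6 by reference.
- **SAP 8.2.5.1.1**, Estimand 7a: an MMRM "including terms for treatment, visit, baseline PASI score (as a continuous covariate), a treatment by visit interaction with an unstructured (UN) covariance matrix", again with elimination. SAP 8.2.5.2.1 and 8.2.6.1 carry it to Estimands 7b, 8a and 8b.

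The table that opens SAP Section 8 repeats the rule. The logistic and GEE models report conditional odds ratios; the MMRMs report differences in means. The Estimand 1a test in SAP 8.1.1.1 is Fisher's exact or chi-squared, without covariates.

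**The concern.** Two patients with different covariates can share the same treatment odds ratio while the odds ratio averaged over them is closer to 1. This is non-collapsibility, and it arises without any confounding. The covariate list is therefore part of the definition of a conditional odds ratio. If p-values from the trial choose the list, the definition is settled after the data are seen.

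Each model also selects for itself. PASI-75 at Week 12 is analysed both in the logistic model of 8.1.2.1 and in the Estimand 5b GEE of 8.2.3.1, so one endpoint at one visit could have two adjusted odds ratios conditioned on different covariates. PASI-50, PASI-90, PASI-100 and sPGA can differ again. BMI is computed from weight and height (SAP 6.1), so the two overlap and can displace each other by chance.

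What is at stake is a clearly defined adjusted odds ratio that can be compared across endpoints. It matters most for Estimands 5a-5d and 6, where the GEE is the main analysis and no covariate-free test stands in front of it.

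**Working it through.** **Plan's own figure.** 5 arms × 45 = 225, which agrees with SAP 4.2. No response rates, effect size or power are visible, so the rates and covariate effects below are assumptions.

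**Number of possible models.** Four covariates, each in or out: 2^4 = 16 per endpoint. If none is prognostic, each stays with probability about 0.2. The chance that at least one stays is 1 - 0.8^4 = 0.59, treating the four as independent; the simulation gave 0.60.

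**Why the list defines the odds ratio.** With assumed rates of 10% and 35%, the unconditional odds ratio is (0.35/0.65)/(0.10/0.90) = 4.85. Holding those rates, the true odds ratio given all covariates was 4.9, 5.2 or 6.2 when the four had no, moderate or strong effect.

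**Simulation.** Five arms of 45, one active arm against placebo, 4,000 runs per scenario (7 to 41 failed fits dropped), BMI-weight correlation about 0.8 (assumed). All models contain treatment, baseline PASI, previous biologic therapy and region. Model A stops there, B adds SAP elimination at 0.2, and C always keeps all four. The factor is exp(|difference in log odds ratio|), 90th percentile.

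| Effect of the four | Power A | Power B | Power C | Factor, B v A | Factor, B v C |
|---|---|---|---|---|---|
| None | 83.0% | 83.2% | 82.8% | 1.13 | 1.08 |
| Moderate | 81.7% | 83.0% | 82.7% | 1.35 | 1.07 |
| Strong | 83.4% | 88.0% | 87.9% | 1.92 | 1.08 |

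- *Covariate sets.* Between 13 and 16 of the 16 sets occurred, depending on the scenario.
- *Power.* B exceeds C by 0.1 to 0.4 points. The Monte Carlo standard error of one power figure is √(0.83 × 0.17/4000) = 0.6 points.
- *Gap with strong effects.* Mean log odds ratio 2.01 (B) against 1.71 (A), that is exp(2.01) ≈ 7.4 against exp(1.71) ≈ 5.5. Most of this is non-collapsibility.
- *Type I error* (15% v 15%): B 3.8-5.0%, C 3.9-4.8%.
- *Coverage* of the full conditional odds ratio by 95% intervals: B 95.0-96.8%, C 95.2-96.8%.
- *Significance* differed between B and C in 0.5-1.3% of trials, and between B and A in 0.8-8.5%.

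A separate simulation with the same arm size gave 12 to 16 sets, logistic power within 0.3 points of model C, and odds ratios about 0.92 to 1.09 times the model C value.

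**Linear stand-in for the MMRM** (one visit, 6,000 runs). Power for A, B and C was 80.2, 80.2 and 79.7% (no effect), 78.7, 80.6 and 79.9% (moderate), and 72.1, 80.0 and 79.7% (strong). The mean estimate was 0.60 in every model, so selection does not change what is estimated. From the standard errors, the four covariates explain about 1 - (0.212/0.218)² = 5% of residual variance in the moderate case and 1 - (0.213/0.236)² = 19% in the strong case. In the separate simulation the linear difference between B and C was 1.2 points or less.

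The GEE was not simulated. The logistic results are taken as a guide to it.

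**The case against.** The strongest reply is that the procedure is prespecified: candidates, direction, threshold and always-kept terms are all written down. The logistic model is also secondary within Estimand 1b. It follows the strata-adjusted result, and the protocol synopsis makes it optional. This stands, and it protects the Week 12 PASI-75 conclusion. It does not protect Estimands 5a-5d and 6, where the selected GEE is the main analysis. A fixed procedure is also not a fixed estimand when the effect measure is non-collapsible.

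The second reply concerns size. At 10% v 35% with 45 per arm, the standard error of the log odds ratio is √(1/4.5 + 1/40.5 + 1/15.75 + 1/29.25) = 0.59, so the 95% interval spans a factor of exp(1.96 × 0.59) ≈ 3.2 each way. A shift of 1.08 is small beside that. This stands too: the case rests on definition and comparability, not on error rates.

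Third, the contents page lists sensitivity and supplementary analyses for Estimand 1b that are not in the public text, and a fixed-covariate check may be among them. That is possible, but it would not settle the main-analysis covariates. The protocol also calls its analyses descriptive and exploratory (Section 9.3), which lowers the stakes but not the value of a clear definition.

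**Conclusion.** The point holds in limited form. Four covariates are chosen by the data in each model, so the conditional odds ratio in the logistic and GEE models is not fixed beforehand and may not be comparable across endpoints. The movement is about 1.07-1.08 against a fixed full model, and 1.13-1.92 against the always-kept terms, depending on how prognostic the four are. These sizes rest on assumed response rates, covariate effects and BMI-weight correlation.

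A reader might infer more, and the documents and the check do not support it:
- *That the primary result is not prespecified.* The Estimand 1a test and the strata-adjusted Estimand 1b result involve no elimination.
- *That false positives rise or intervals are too short.* Neither appeared in the simulations.
- *That the MMRM target shifts.* A mean difference is collapsible; only consistency is at issue.
- *That selection gains nothing.* It gains nothing material over fixing the same covariates. Over the always-kept terms alone it gained 1.3 to 4.6 points (logistic) and 1.9 to 7.9 points (linear) when the four were prognostic.

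**What to change.** Delete the backward-elimination step from SAP 8.1.2.1, 8.2.3.1, 8.2.5.1.1 and the Section 8 table. Before unblinding, name one list for all models: treatment, the baseline value, previous biologic therapy, region, and whichever of age, sex and one of weight or BMI the sponsor judges prognostic. Add visit and treatment-by-visit in the repeated-measures models. State which baseline score is meant for sPGA and BSA, since those sections only refer back to the PASI models. The choice between weight and BMI is the sponsor's; the documents give no evidence for either.

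The cost is SAP wording and simpler programs, with no change to conduct, data or sample size. The downside is about 1 point of power or less compared with selection when the prognostic covariates are on the list. The loss is somewhat larger if a strongly prognostic one is left off: leaving off all four in the strong scenario cost 4.6 points (logistic) or 7.9 points (linear). A short list is also prudent because SAP 8.2.3.1 falls back to unadjusted odds ratios if the GEE does not converge.

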#### 8.2. Secondary Efficacy Endpoints

The secondary efficacy endpoints are analyzed as follow:

#### 8.2.1. Proportion of participants in each DC-806 treatment group achieving PASI-75 at Week 12 (Estimand 3a/3b)

The primary endpoint for Estimand 3a/3b is the same as Estimand 1a/1b.

#### 8.2.1.1. Estimand 3a

#### 8.2.1.1.1. Main Analysis Approach

A participant receiving any prohibited medication or discontinuing the treatment due to related adverse event or requirement for prohibited medication prior to Week 12 visit will be considered as a non-responder (Composite strategy). If a participant discontinued treatment for reasons other than related adverse event or requirement for prohibited medication, PASI scores reported after the treatment discontinuation date will be treated as missing (Hypothetical strategy). If a participant experienced any treatment interruption, PASI score reported after the treatment interruption will be used as reported (Treatment policy).

Participants without Week 12 PASI score (either due to hypothetical strategy implementation or missed visit) will be considered as non-responder.

A Fisher's exact or Chi-squared test based on the observed counts will be performed to assess a difference between active treatment groups in PASI-75 at Week 12 for the following comparisons on the FAS:

#### Comparison 1

H0: PASI-75 at Week 12  $_{DC-806\ 800mg}$  = PASI-75 at Week 12  $_{DC-806\ 200mg}$ H1: PASI-75 at Week 12  $_{DC-806\ 800mg} \neq$  PASI-75 at Week 12  $_{DC-806\ 200mg}$ 

#### Comparison 2

H0: PASI-75 at Week 12  $_{DC-806\ 800mg}$  = PASI-75 at Week 12  $_{DC-806\ 400mg}$ H1: PASI-75 at Week 12  $_{DC-806\ 800mg} \neq$  PASI-75 at Week 12  $_{DC-806\ 400mg}$ 

#### **Comparison 3**

H0: PASI-75 at Week 12  $_{DC-806\ 800mg}$  = PASI-75 at Week 12  $_{DC-806\ 600mg}$ H1: PASI-75 at Week 12  $_{DC-806\ 800mg} \neq$  PASI-75 at Week 12  $_{DC-806\ 600mg}$ 

#### **Comparison 4**

H0: PASI-75 at Week 12  $_{DC-806\ 600mg}$  = PASI-75 at Week 12  $_{DC-806\ 200mg}$ H1: PASI-75 at Week 12  $_{DC-806\ 600mg} \neq$  PASI-75 at Week 12  $_{DC-806\ 200mg}$ 

#### **Comparison 5**

H0: PASI-75 at Week 12  $_{DC-806\ 600mg}$  = PASI-75 at Week 12  $_{DC-806\ 400mg}$ H1: PASI-75 at Week 12  $_{DC-806\ 600mg} \neq$  PASI-75 at Week 12  $_{DC-806\ 400mg}$ 

#### Comparison 6

H0: PASI-75 at Week 12  $_{DC-806\ 400mg}$  = PASI-75 at Week 12  $_{DC-806\ 200mg}$ H1: PASI-75 at Week 12  $_{DC-806\ 400mg} \neq$  PASI-75 at Week 12  $_{DC-806\ 200mg}$ 

The number and percentage of participants who are defined as PASI-75 responder will be presented by active treatment group. The p-value and unconditional odds ratio with its corresponding 95% CI will be presented in the lower dose treatment group compared to the higher dose treatment group.

All comparisons will be performed in a prespecified hierarchical procedure starting from the highest dose regimen to the lowest dose regimen.

#### 8.2.1.1.4. Additional Supplementary Analyses

A Cochran-Armitage trend test will be conducted to assess a positive trend between DC-806 dose regimens and PASI-75 at Week 12. The two-sided p-value test against either an increasing or decreasing alternative will be provided.

A participant receiving any prohibited medication or discontinuing the treatment due to related adverse event or requirement for prohibited medication prior to Week 12 visit or participants with missing Week 12 PASI score will be considered as a non-responder.

#### 8.2.1.2. Estimand 3b

#### 8.2.1.2.1. Main Analysis Approach

A participant receiving any prohibited medication or discontinuing the treatment due to related adverse event or requirement for prohibited medication prior to Week 12 visit will be considered as a non-responder (Composite strategy). If a participant discontinued treatment for reasons other than related adverse event or requirement for prohibited medication, PASI scores reported after the treatment discontinuation date will be treated as missing (Hypothetical strategy). If a participant experienced any treatment interruption, PASI score reported after the treatment interruption will be used as reported (Treatment policy).

Participants without Week 12 PASI score (either due to hypothetical strategy implementation or missed visit) will be considered as non-responder.

The number and proportion of participants with PASI-75 with corresponding 95% CI will be presented by active treatment group. The p-value, conditional odds ratio with its corresponding 95% CI, strata-adjusted difference in proportions between active treatment groups and its corresponding 95% CI based on the large sample approximation method for binary data using Mantel-Haenszel strata weights (Mantel, Haenszel 1959) and the Sato variance estimator (Sato 1989) will be presented.

# 8.2.2. Proportion of participants achieving a sPGA score of 0 or 1 with ≥2 grade improvement from Baseline at Week 12 (Estimands 4a and 4b)

Participants with sPGA score of 0 or 1 with  $\geq 2$  grade improvement from baseline will be plotted over time by treatment group.

#### 8.2.2.1. Main Analysis Approach

Similar methods and intercurrent event strategies as applied in the main analysis provided for Estimand 1a/1b analysis will be used to evaluate proportion of participants achieving a sPGA score of 0 (clear) or 1 (almost clear) with  $\geq 2$  grade improvement from Baseline at Week 12 on FAS. (see Sections 8.1.1.1 and 8.1.2.1).

# 8.2.3. Proportion of participants achieving ≥50%, ≥75%, ≥90%, and 100% reduction in PASI score (PASI-50, PASI-75, PASI-90, and PASI-100, respectively) at scheduled timepoints (Estimands 5a, 5b, 5c, 5d)

#### 8.2.3.1. Main Analysis Approach

A participant receiving any prohibited medication or discontinuing the treatment due to related adverse event or requirement for prohibited medication will be considered as a non-responder at scheduled timepoints following the event (Composite strategy). If a participant discontinued treatment for reasons other than related adverse event or requirement for prohibited medication, PASI scores reported after the treatment discontinuation date will be treated as missing (Hypothetical strategy). If a participant experienced any treatment interruption, PASI score reported after the treatment interruption will be used as reported (Treatment policy).

Participants without PASI score at each scheduled visit (either due to hypothetical strategy implementation or missed visit) will be considered as non-responder.

The following analyses will be performed using generalized estimating equation (GEE) as an extension of the logistic regression model with treatment, visit and baseline PASI score (as a continuous covariate) as covariates and a treatment by visit interaction. The following additional covariates will be tested in the model using backward elimination with a significance level of 0.2 to retain the covariates in the model: age, BMI and weight as continuous covariates, sex, previous biologic therapy (Yes/No) (as per IRT) and geographic region (North America/Western Europe vs. Eastern Europe) (as per IRT). At the very least, previous biologic therapy and geographic region will be retained in the model. Of note, visits from the earliest timepoint with at least one responder will be included in the model. e.g. if the first responder is on Day 15, all GEE models will include visits from Day 15.

- Participants achieving ≥50% reduction in PASI score (PASI-50) at scheduled timepoints up to Week 12 by treatment group for the FAS. (Estimand 5a)
- Participants achieving ≥75% reduction in PASI score (PASI-75) at scheduled timepoints up to Week 12 by treatment group for the FAS. (Estimand 5b)
- Participants achieving ≥90% reduction in PASI score (PASI-90) at scheduled timepoints up to Week 12 by treatment group for the FAS. (Estimand 5c)
- Participants achieving 100% reduction in PASI score (PASI-100) at scheduled timepoints up to Week 12 by treatment group for the FAS. (Estimand 5d)

The conditional odds ratio, with placebo as reference group, and their corresponding 2-sided 95% CI will be presented.

In case of non-convergence, unadjusted odds ratio will be estimated separately for each scheduled timepoint.

Proportion of participants with PASI-50, PASI-75, PASI-90, and PASI-100 based on descriptive statistics with observed values will be plotted over time by treatment group.

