To compare the efficacy of multiple doses of DC-806 versus placebo on additional efficacy endpoints in adult participants with moderate to severe plaque psoriasis	Proportion of participants achieving an sPGA score of 0 (clear) or 1 (almost clear) with ≥2 grade improvement from Baseline at Week 12	Estimand 3b: As above but with odds ratio as population-level summary. Estimand 4a: This estimand is intended to provide a population-level estimate of the anti-psoriatic effect of DC-806 versus Placebo on a binary composite responder endpoint (sPGA score of 0 [clear] or 1 [almost clear]) with ≥2 grade improvement from Baseline) at Week 12 without the benefit of other background anti-psoriasis therapy regardless of the use of topical bland moisturizers, or emollients, or bland shampoos as needed and regardless of treatment interruption Target Population: Same as in E1a Treatment Conditions: Same as in E1a Variable: Same as in E1a, but for sPGA score of 0 or 1 with ≥2 grade improvement from Baseline at Week 12 Strategies for Intercurrent Events: Same as in E1a Population-Level Summary: Difference in the response rates at Week 12 Estimand 4b: As above but with odds ratio as population-level summary		
	Proportion of participants achieving ≥50%, ≥75%, ≥90%, and 100% reduction in PASI score (PASI-50, PASI-75, PASI-90, and PASI-100, respectively) at all scheduled timepoints	Estimand 5a: This estimand is intended to provide a population-level estimate of the anti-psoriatic effect of DC-806 versus Placebo on a binary composite responder endpoint (PASI-50) at all scheduled timepoints without the benefit of other background anti-psoriasis therapy regardless of the use of topical bland moisturizers or emollients or bland shampoos as needed and regardless of treatment interruption • Target Population: Same as in E1a • Treatment Conditions: Same as in E1a • Variable: Same as in E1a, but for PASI-50 at all scheduled timepoints up to Week 12 • Strategies for Intercurrent Events: Same as in E1a • Population-Level Summary: Odds ratio Estimand 5b: As above but with PASI-75 as variable Estimand 5c: As above but with PASI-90 as variable Estimand 5d: As above but with PASI-100 as variable		

Confidential Page 30 of 91

Objectives	Endpoints	Estimands			
	Proportion of	Estimand 6: This estimand is intended to provide a population-level estimate of the anti-psoriatic effect of			

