9.3.5.2 Secondary Efficacy Analyses

Similar analyses as in primary efficacy analyses will be performed to compare any 2 DC-806 dose regimens.

A Cochran-Armitage trend test will be conducted to assess a positive trend between DC-806 dose regimens and PASI-75 at Week 12.

The response rate in PASI-50, PASI-75, PASI-90, and PASI-100 will be summarized by treatment group and visit and will be analyzed using a repeated measure model when applicable.

The proportion of participants with an sPGA score of "0" or "1" will be analyzed similarly to the primary analyses. sPGA and DLQI score will be tabulated by treatment group and visit; the corresponding changes from Baseline and percent change from Baseline will be calculated and summarized.

For continuous secondary endpoints (eg, change from Baseline to Week 12 in PASI scores), point estimates and 2-sided 95% CIs for mean change from Baseline within each treatment group will be provided. For binary endpoints (eg, response rate in PASI and sPGA), point estimates of the response rate and 2-sided 95% CIs will be provided using normal approximation within each treatment group.

There will be no adjustment for multiplicity. All comparisons will be performed in a prespecified hierarchical procedure starting from the highest dose regimen to the lowest dose regimen.

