# 8.2.4.1. Main Analysis Approach

Similar methods and intercurrent event strategies as applied in the main analysis provided for Estimand 5 analysis will be used to evaluate proportion of participants achieving a sPGA score of 0 (clear) or 1 (almost clear) with  $\geq$ 2 grade improvement from Baseline at scheduled timepoints up to Week 12 on FAS (see Section 8.2.3.1).

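### Estimands 5a–5d and 6: a visit with no placebo responders can enter the GEE, and neither the model nor its fallback says how the odds ratio is then obtained; the protocol's within-arm interval also fails at zero

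*SAP*

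**What the plan says.** SAP 8.2.3.1 models PASI-50, -75, -90 and -100 with a logistic GEE containing treatment, visit, their interaction, baseline PASI and further covariates.

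- **Visit entry:** "visits from the earliest timepoint with at least one responder will be included in the model". The example adds that "if the first responder is on Day 15, all GEE models will include visits from Day 15".
- **Missing scores:** "Participants without PASI score at each scheduled visit (either due to hypothetical strategy implementation or missed visit) will be considered as non-responder". The denominator is therefore the whole arm, about 45 (SAP 4.2).
- **Output:** "The conditional odds ratio, with placebo as reference group, and their corresponding 2-sided 95% CI will be presented".
- **Fallback:** "In case of non-convergence, unadjusted odds ratio will be estimated separately for each scheduled timepoint".

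SAP 8.2.4.1 carries this over to Estimand 6: "Similar methods and intercurrent event strategies as applied in the main analysis provided for Estimand 5 analysis will be used". Protocol 3.0 names the summary for Estimands 5a–5d and for Estimand 6 as "Population-Level Summary: Odds ratio", and SAP 2.2 agrees.

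On within-arm rates, Protocol 9.3.5.2 and the synopsis say that "point estimates of the response rate and 2-sided 95% CIs will be provided using normal approximation within each treatment group". SAP 8.1 promises a 95% CI for the Week 12 PASI-75 proportion without naming a method.

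**The concern.** The interaction gives each arm-by-visit cell its own parameter, so a placebo cell with no responders has to be estimated on the logit scale, and the estimate runs off to minus infinity. The entry rule does not prevent this because it does not look at the placebo count. Read literally, the example sets one start visit for all the models, so an early PASI-50 responder could bring that visit into the PASI-90 and PASI-100 models as well.

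The fallback does not repair it. It meets the same empty cell, and its trigger is a software flag rather than the count. Two outcomes are then possible:

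- The fit is flagged as converged and the table carries a meaningless odds ratio.
- The whole fit fails, and every visit, Week 12 included, moves to an unadjusted odds ratio.

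Which one occurs depends on the working correlation, which the main-analysis text does not give. If an analyst then chooses a zero-cell method after seeing the data, that choice can decide whether the interval excludes 1. The within-arm interval has a related weakness: at zero responders it claims certainty.

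**Working it through.** The documents give no response rates or effect sizes for these endpoints, so there is no planned figure to reproduce. The arm size of about 45 and the two-sided 95% level (SAP 4 and 4.2) are the plan's. All response rates below are assumptions.

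**1. Chance of a zero placebo count.** P(0/45) = (1 − p)^45.

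| True placebo rate | 1% | 2% | 3% | 5% | 10% |
|---|---|---|---|---|---|
| P(0/45) | 64% | 40% | 25% | 10% | 1% |

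**2. No finite odds ratio.** With 0/45, the placebo log-likelihood at logit b is −45·log(1 + e^b). It is −0.82 at b = −4, −0.002 at b = −10 and about 0 at b = −20, so it rises without reaching a maximum. The unadjusted odds ratio is a·45 / ((45 − a)·0): infinite for a > 0, and 0/0 if the active arm is also zero. The argument is exact for the unadjusted odds ratio and for independence working correlation. A GEE is not strictly maximum likelihood under other correlations.

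**3. The unnamed method matters.** For a/45 against 0/45:

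| a | Fisher p | Exact conditional lower limit (2.5% tail) | Lower limit, 0.5 added to each cell |
|---|---|---|---|
| 5 | 0.056 | 0.96 | 0.66 |
| 6 | 0.026 | 1.26 | 0.82 |
| 7 | 0.012 | 1.57 | 0.98 |
| 10 | 0.0011 | 2.62 | 1.52 |

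At 6/45 and 7/45 the two methods disagree on whether 1 is excluded. The tail matters too: at 5/45 the exact lower limit is 0.96 with 2.5% in the tail and 1.28 with 5%.

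**4. GEE behaviour.** Simulated trials had five arms of 45 and a model with arm by visit, baseline PASI, prior biologic and region. Assumed placebo rates were 0.3, 0.7, 1.5, 3 and 6% over the five visits, with active arms rising to 20, 25, 35 and 42% at Week 12. Latent correlation was 0.4 or 0.7. There were 40 data sets per run, all selected to have placebo zero at an earlier visit and every arm non-zero at Week 12, and all fitted in statsmodels. Usable means finite, |log OR| < 8 and SE < 5 for all four doses at Week 12.

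- *Independence:* flagged converged, with Week 12 usable, in 40/40 in every run. In the three-visit run at correlation 0.4, however, the log odds ratio at zero-cell visits was 22 to 26, with SE 42 to 926 or not computable (77 of 192 pair-visits). No interval excluded 1.
- *Exchangeable:* flagged converged in 26/40 and 23/40 (three visits, correlation 0.4 and 0.7) and in 5 to 11 of 40 (five visits). Week 12 was usable in 26/40, 22/40 and 5 to 11 of 40.
- *Zero-cell visits removed:* 40/40 under both correlations. Under independence, removal moved the Week 12 log odds ratio by at most 0.20.

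**5. Within-arm interval at n = 45.** Wald is p̂ ± 1.96·√(p̂(1 − p̂)/45).

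| Responders | Wald | Wilson |
|---|---|---|
| 0 | [0, 0] | [0, 7.9%] |
| 1 | [−2.1, 6.5%] | [0.4, 11.6%] |
| 3 | [−0.6, 14.0%] | [2.3, 17.9%] |

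Exact binomial coverage at true rates of 1, 2 and 3% is 36, 60 and 74% for Wald and 93, 94 and 95% for Wilson. At 10% it is 94% and 96%.

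**The case against.** The stakes are limited. Protocol 9.3 calls the analysis descriptive and exploratory, these are secondary estimands, and rates are still summarised by visit (Protocol 9.3.5.2) and plotted (SAP 8.2.3.1). The SAP already has an entry rule and a fallback. The simulated failures rest on invented rates, on data sets selected for an early zero, and on one package; the alarming ones need an exchangeable correlation that the SAP does not state. Normal approximation need not mean Wald, and SAP 8.2.3.1 itself schedules no within-arm interval. All of this stands, and it limits the weight of the point. It does not supply a method for the zero cell.

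A reader might infer three stronger things that the documents do not support:

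- *That the plan has no sparse-data rule anywhere.* The contents list SAP 8.2.3.2, 8.2.3.3, 8.2.4.2 and 8.2.4.3, whose text is not in the public version. Only the main-analysis text can be judged.
- *That the primary result is at risk, or that a dose effect would be hidden.* The Week 12 PASI-75 and sPGA tests use Fisher or chi-squared, and the counts stay visible.
- *That a visit should leave the model whenever any arm is zero.* That goes too far. In 40 simulated data sets with an active-arm zero and a non-zero placebo count (assumed placebo rates 1.5, 3 and 6%, independence), all 112 pairs without a zero cell at the affected visits kept a usable adjusted odds ratio with the visit retained, as did all 160 Week 12 pairs. Such a rule would also remove the adjusted Week 12 PASI-100 odds ratio for every dose whenever placebo was 0/45.

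**Conclusion.** The point holds for the main-analysis text of Estimands 5a–5d and 6. The entry rule admits visits with 0/45 on placebo. At those visits the named summary is not finite under independence or in the unadjusted fallback, and is undefined if the active arm is also zero. The fallback may never be triggered, and it names no zero-cell method. Under an exchangeable correlation an early zero can make the whole fit fail and cost Week 12 its adjusted odds ratio.

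How often this arises depends on placebo rates that the documents do not give: likely at 1 to 2%, rare at 10%. How the software behaves may differ in SAS. The separate point on the within-arm interval rests on the protocol wording read in its usual Wald sense; if a score interval was meant, it should be named. The change is worth making because it is specific and cheap, but it does not bear on the primary analysis.

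**What to change.** 1. **Within-arm rates:** name the Wilson interval in the SAP, and align Protocol 9.3.5.2 and the synopsis at the next amendment.
2. **Model (SAP 8.2.3.1, carried to 8.2.4.1):** state an independence working correlation with robust standard errors. Apply the visit-entry rule separately for each PASI threshold and for sPGA. Keep the visit for every active–placebo pair without a zero cell; do not drop it for all doses because one arm is zero.
3. **Zero-cell pairs:** where either arm of a pair has no responders or no non-responders at a visit, do not report the GEE odds ratio, whether or not the fit is flagged as converged. Report counts with the unadjusted exact conditional odds ratio and exact 95% CI, 2.5% in each tail, giving only the finite limit where the estimate is infinite or zero. Where both arms have no responders, or both have no non-responders, report counts only. Use the same exact method if a GEE fails to converge.

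The cost is wording; no new data are needed. Exact intervals are conservative: coverage was 99% at assumed placebo/active rates of 1/10, 2/20, 3/15 and 2/5%. Zero-cell pairs carry an unadjusted odds ratio on a different scale from the GEE's conditional one, so the table should label them. Independence may lose a little efficiency.
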